7.4. Gilead Reporting Requirements

Depending on relevant local legislation or regulations, including the applicable US FDA Code of Federal Regulations (CFR), the EU Clinical Trials Directive (2001/20/EC) and relevant updates, and other country-specific legislation or regulations, Gilead may be required to expedite to worldwide regulatory agencies reports of SAEs, serious adverse drug reactions (SADRs), or SUSARs. In accordance with the EU Clinical Trials Directive (2001/20/EC), Gilead or a specified designee will notify worldwide regulatory agencies and the relevant IEC in concerned Member States of applicable SUSARs as outlined in current regulations.

Assessment of expectedness for SAEs will be determined by Gilead using reference safety information specified in the IB or relevant local label as applicable.

All investigators will receive a safety letter notifying them of relevant SUSAR reports associated with any study IMP. The investigator should notify the IRB or IEC of SUSAR reports as soon as is practical, where this is required by local regulatory agencies, and in accordance with the local institutional policy.

7.5. Clinical Laboratory Abnormalities and Other Abnormal Assessments as Adverse Events or Serious Adverse Events

Laboratory abnormalities are usually not recorded as AEs or SAEs. However, laboratory abnormalities (eg, clinical chemistry, hematology, and urinalysis) independent of the underlying medical condition that require medical or surgical intervention or lead to investigational medicinal product interruption or discontinuation must be recorded as an AE, as well as an SAE, if applicable. In addition, laboratory or other abnormal assessments (eg, ECG, x-rays, vital signs) that are associated with signs and/or symptoms must be recorded as an AE or SAE if they meet the definition of an AE (or SAE) as described in Sections [7.1.1](#) and [7.1.2](#). If the laboratory abnormality is part of a syndrome, record the syndrome or diagnosis (ie, anemia) not the laboratory result (ie, decreased hemoglobin).

Severity should be recorded and graded according to the CTCAE Grading Scale for Severity of Adverse Events and Laboratory Abnormalities ([Appendix 8](#)). For AEs associated with laboratory abnormalities, the event should be graded on the basis of the clinical severity in the context of the underlying conditions; this may or may not be in agreement with the grading of the laboratory abnormality.

7.6. Toxicity Management

All clinical and clinically significant laboratory toxicities will be managed according to uniform guidelines detailed in [Appendix 3](#), and as outlined below.

Refer to Section [3.5](#), Criteria for Study Drug Interruption or Discontinuation, for additional specific discontinuation criteria. Specific toxicity discontinuation criteria in Section [3.5](#) supersede the below general toxicity guidelines, and in general, where discrepancy is present, the more conservative criteria should apply. The Study Medical Monitor should be consulted prior to study drug discontinuation when medically feasible.

7.6.1. Grades 1 and 2 Laboratory Abnormality or Clinical Event

Continue study drug at the discretion of the investigator.

7.6.2. Grade 3 Laboratory Abnormality or Clinical Event

For a Grade 3 clinically significant laboratory abnormality or clinical event, IMP may be continued if the event is considered to be unrelated to IMP.

For a Grade 3 clinical event, or clinically significant laboratory abnormality confirmed by repeat testing, that is considered to be related to IMP, IMP should be withheld until the toxicity returns to \leq Grade 2.

If a laboratory abnormality recurs to \geq Grade 3 following re-challenge with IMP and is considered related to IMP, then IMP should be permanently discontinued and the subject managed according to local practice. Recurrence of laboratory abnormalities considered unrelated to IMP may not require permanent discontinuation.

7.6.3. Grade 4 Laboratory Abnormality or Clinical Event

For a Grade 4 clinical event or clinically significant Grade 4 laboratory abnormality confirmed by repeat testing that is considered related to IMP, IMP should be permanently discontinued and the subject managed according to local practice. The subject should be followed as clinically indicated until the laboratory abnormality returns to baseline or is otherwise explained, whichever occurs first. A clinically significant Grade 4 laboratory abnormality that is not confirmed by repeat testing should be managed according to the algorithm for the new toxicity grade.

Investigational medicinal product may be continued without dose interruption for a clinically non-significant Grade 4 laboratory abnormality (eg, Grade 4 creatine kinase [CK] after strenuous exercise or triglyceride elevation that is nonfasting or that can be medically managed) or a clinical event considered unrelated to IMP.

Treatment-emergent toxicities will be noted by the investigator and brought to the attention of the Study Medical Monitor, who will have a discussion with the investigator and decide the appropriate course of action. Whether or not considered treatment-related, all subjects experiencing AEs must be monitored periodically until symptoms subside, any abnormal laboratory values have resolved or returned to baseline levels or they are considered irreversible, or until there is a satisfactory explanation for the changes observed.

Any questions regarding toxicity management should be directed to the Study Medical Monitor.

7.7. Special Situations Reports

7.7.1. Definitions of Special Situations

Special situation reports include all reports of medication error, abuse, misuse, overdose, occupational exposure, drug interactions, exposure via breastfeeding, unexpected benefit, transmission of infectious agents via the product, product complaints, counterfeit or falsified medicine, and pregnancy reports regardless of an associated AE.

Medication error is any unintentional error in the prescribing, dispensing, preparation for administration or administration of an investigational product while the medication is in the control of a health care professional, patient, or consumer. Medication errors may be classified as a medication error without an AE, which includes situations of missed dose; medication error with an AE; intercepted medication error; or potential medication error.

Abuse is defined as persistent or sporadic intentional excessive use of an investigational product by a subject.

Misuse is defined as any intentional and inappropriate use of an investigational product that is not in accordance with the protocol instructions or the local prescribing information.

An overdose is defined as an accidental or intentional administration of a quantity of an investigational product given per administration or cumulatively which is above the maximum recommended dose as per protocol or in the product labelling (as it applies to the daily dose of the subject in question). In cases of a discrepancy in drug accountability, overdose will be established only when it is clear that the subject has taken the excess dose(s). Overdose cannot be established when the subject cannot account for the discrepancy except in cases in which the investigator has reason to suspect that the subject has taken the additional dose(s).

Occupational exposure is defined as exposure to an investigational product as a result of one's professional or non-professional occupation.

Drug interaction is defined as any drug/drug, drug/food, or drug/device interaction.

Unexpected benefit is defined as an unintended therapeutic effect where the results are judged to be desirable and beneficial.

Transmission of infectious agents is defined as any suspected transmission of an infected agent through a GSI investigational product.

Product complaint is defined as complaints arising from potential deviations in the manufacture, packaging, or distribution of the investigational product.

Counterfeit or falsified medicine: Any investigational product with a false representation of: a) its identity, b) its source, or c) its history.

7.7.2. Instructions for Reporting Special Situations

7.7.2.1. Instructions for Reporting Pregnancies

The investigator should report pregnancies in female study subjects that are identified after initiation of study drug and throughout the study, including the post study drug follow-up period, to the Gilead PVE using the pregnancy report form within 24 hours of becoming aware of the pregnancy.

Refer to Section 7.3 and the eCRF completion guidelines for full instructions on the mechanism of pregnancy reporting.

The pregnancy itself is not considered an AE nor is an induced elective abortion to terminate a pregnancy without medical reasons.

Any premature termination of pregnancy (eg, a spontaneous abortion, an induced therapeutic abortion due to complications or other medical reasons) must be reported within 24 hours as an SAE. The underlying medical reason for this procedure should be recorded as the AE term.

A spontaneous abortion is always considered to be an SAE and will be reported as described in Section 7.3.2. Furthermore, any SAE occurring as an adverse pregnancy outcome post study must be reported to Gilead PVE.

The subject should receive appropriate monitoring and care until the conclusion of the pregnancy. The outcome should be reported to Gilead PVE using the pregnancy outcome report form. If the end of the pregnancy occurs after the study has been completed, the outcome should be reported directly to Gilead PVE. Gilead PVE contact information is as follows:

Gilead PVE:	Fax:	PPD
	E-mail:	PPD

Pregnancies of female partners of male study subjects exposed to Gilead or other study drugs must also be reported and relevant information should be submitted to Gilead PVE using the pregnancy and pregnancy outcome forms within 24 hours. If the end of the pregnancy occurs after the study has been completed, the outcome should be reported directly to Gilead PVE.

Gilead PVE:	Fax:	PPD
	E-mail:	PPD

Refer to Appendix 9 for Pregnancy Precautions, Definition for Female of Childbearing Potential, and Contraceptive Requirements.

7.7.2.2. Reporting Other Special Situations

All other special situation reports must be reported on the special situations report form and forwarded to Gilead PVE within 24 hours of the investigator becoming aware of the situation. These reports must consist of situations that involve study drug and/or Gilead concomitant medications, but do not apply to non-Gilead concomitant medications.

Special situations involving non-Gilead concomitant medications do not need to be reported on the special situations report form; however, for special situations that result in AEs due to a non-Gilead concomitant medication, the AE must be reported as an AE.

Any inappropriate use of concomitant medications prohibited by this protocol should not be reported as “misuse,” but may be more appropriately documented as a protocol deviation.

Refer to Section [7.3](#) and the eCRF completion guidelines for full instructions on special situations reporting.

All clinical sequelae in relation to these special situation reports will be reported as AEs or SAEs at the same time using the AE eCRF and/or the SAE report form. Details of the symptoms and signs, clinical management, and outcome will be reported, when available.

8. STATISTICAL CONSIDERATIONS

8.1. Analysis Objectives and Endpoints

8.1.1. Analysis Objectives

The primary objective is:

- To evaluate the efficacy of filgotinib as compared to placebo in establishing combined fistula response at Week 24

The secondary objectives are:

- To evaluate the efficacy of filgotinib as compared to placebo in establishing combined fistula remission at Week 24
- To assess the time to clinical fistula response
- To assess the time to clinical fistula remission
- To evaluate the efficacy of filgotinib as compared to placebo in establishing proctitis remission at Week 24, in subjects that had moderately to severely active proctitis at baseline
- To evaluate the safety and tolerability of filgotinib

CCI

8.1.2. Primary Endpoint

[figure not shown]
The primary efficacy endpoint is the proportion of subjects establishing combined fistula response at Week 24

8.1.3. Secondary Endpoints

The secondary efficacy endpoints are:

- Proportion of subjects establishing combined fistula remission at Week 24
- Time to clinical fistula response
- Time to clinical fistula remission
- Proportion of subjects achieving proctitis remission at Week 24, in subjects that had moderately to severely active proctitis at baseline

CCI

8.2. Analysis Conventions

8.2.1. Analysis Sets

8.2.1.1. Efficacy

The primary analysis set for efficacy analyses will be the Full Analysis Set (FAS), defined as all randomized subjects who received at least one dose of study drug.

8.2.1.2. Safety

The primary analysis set for safety analyses is the Safety Analysis Set, defined as all subjects who received at least one dose of study drug.

CCI [REDACTED]

[REDACTED]

CCI [REDACTED]

[REDACTED]

8.3. Data Handling Conventions

Values for missing safety laboratory data will not be imputed. However, a missing baseline result will be replaced with a screening result, if available. If no pre-treatment laboratory value is available, the baseline value will be assumed to be normal (ie, no grade [Grade 0]) for the summary of graded laboratory abnormalities. If safety laboratory results for a subject are missing for any reason at a time point, the subject will be excluded from the calculation of summary statistics for that time point.

Values for missing vital signs data will not be imputed. However, a missing baseline result will be replaced with a screening result, if available.

CCI [REDACTED]

Laboratory data that are continuous in nature but are less than the lower limit of quantitation or above the upper limit of quantitation will be imputed to the value of the lower or upper limit minus or plus one significant digit, respectively (eg, if the result of a continuous laboratory test is < 20, a value of 19 will be assigned; if the result of a continuous laboratory test is < 20.0, a value of 19.9 will be assigned).

CCI [REDACTED]

8.4. Demographic Data and Baseline Characteristics

Demographic and baseline measurements will be summarized separately by treatment group using standard descriptive statistics (n, mean, standard deviation [SD], median, 1st quartile [Q1], 3rd quartile [Q3], minimum, maximum) for continuous variables and number and percentage of subjects for categorical variables.

Demographic summaries will include age, sex, race and ethnicity. Baseline characteristics may include height, weight, body mass index (BMI), CCI [REDACTED], number of years since diagnosis of CD, anatomy of draining perianal fistulae (simple *versus* complex), presence of moderately to severely active proctitis (Yes or No), Receiving vedolizumab therapy concomitantly at Day 1 (Yes or No), fecal calprotectin, fecal lactoferrin, serum CRP, and other variables of interest.

8.5. Efficacy Analysis

8.5.1. Primary Analysis

The number and proportion of subjects establishing combined fistula response at Week 24 for each treatment group will be summarized with corresponding exact 90% CI based on binomial distribution (Clopper-Pearson method). The difference in proportions between each filgotinib dose group and the placebo group will be presented along with the associated 90% CI. Subjects who do not have sufficient measurements to determine efficacy endpoint will be considered failures (ie, non-responder imputation [NRI]). No formal hypothesis testing will be performed.

8.5.2. Secondary Analyses

The same summaries used for the primary endpoint will be utilized for the proportion of subjects establishing combined fistula remission at Week 24. Subjects who do not have sufficient measurements to determine efficacy endpoint will be considered failures (ie, NRI).

For time-to-event secondary endpoints, the summary statistics (eg, median, Q1, Q3) from the Kaplan-Meier method will be provided for each treatment group. The stratified Cox proportional hazards model will be used to estimate the hazard ratio with the corresponding 90% CI.

CCl [REDACTED]

8.6. Safety Analysis

Safety will be evaluated by assessment of clinical laboratory tests, PE, ECG and vital signs measurements at various time points during the study, and by the documentation of AEs. All safety data collected on or after the first dose of study drug administration (Day 1) up to 30 days after permanent discontinuation of study drug will be summarized by treatment group according to the study drug received.

All data collected during the course of the study will be included in data listings.

8.6.1. Extent of Exposure

A subject's extent of exposure to study drug will be generated from the study drug administration page of the eCRF. The number of doses administered and the level of adherence will be summarized by treatment group.

8.6.2. Adverse Events

Adverse events will be coded using the Medical Dictionary for Regulatory Activities (MedDRA). System Organ Class (SOC), High-Level Group Term (HLGT), High-Level Term (HLT), Preferred Term (PT), and Lower-Level Term (LLT) will be attached to the clinical database.

Treatment-Emergent Adverse Events (TEAEs) are defined as 1 or both of the following:

- Any AEs with an onset date of on or after the study drug start date for the entire study (Day 1) and up to 30 days after permanent discontinuation of study drug.
- Any AEs leading to premature discontinuation of study drug.

Summaries (number and percentage of subjects) of TEAEs by SOC and PT will be provided by treatment group. TEAEs will also be summarized by relationship to study drug and severity. In addition, TEAEs leading to premature discontinuation of study drug will be summarized and listed.

8.6.3. Laboratory Evaluations

Selected laboratory data (using conventional units) will be summarized using only observed data. Absolute value and change from baseline at all scheduled time points will be summarized.

Graded laboratory abnormalities will be defined using the grading scheme defined in the Common Terminology Criteria for Adverse Events (CTCAE).

Incidence of treatment-emergent laboratory abnormalities defined as values that increase at least 1 toxicity grade from baseline at any time post baseline will be summarized by treatment group. If baseline data are missing, then any graded abnormality (ie, at least a Grade 1) will be considered treatment-emergent.

8.6.4. Other Safety Evaluations

Individual data for physical examination findings, prior and concomitant medications and medical history will be provided. Twelve-lead ECGs and vital signs measurements will be listed by subject and summarized by incidence of events/abnormalities or descriptive statistics as appropriate.

CCI

CCI

CCI

8.8. Sample Size

A total of approximately 75 subjects are planned to be randomized (2:2:1 ratio); 30 subjects to each of the filgotinib dose groups and 15 subjects to the placebo group. This sample size is considered adequate to assess the safety, tolerability, and efficacy of filgotinib in a descriptive manner.

Table 8-1 provides the exact 90% CI using the binomial distribution for a given combined fistula response rate ranging from 20% to 80%:

Table 8-1. Combined Fistula Response Rates (90% CI)

Number Randomized	Number of Responders	Response rate	Lower Limit of 90% CI	Upper Limit of 90% CI
30	6	20%	9%	36%
30	9	30%	17%	47%
30	12	40%	25%	57%
30	15	50%	34%	66%
30	18	60%	43%	75%
30	21	70%	53%	83%
30	24	80%	64%	91%

CI = confidence interval

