Table 8-1.	Combined Fistula Response Rates (90% CI).....	78

LIST OF IN-TEXT FIGURES

Figure 3-1.	Study Design Schematic	33
-------------	------------------------------	----

PROTOCOL SYNOPSIS

[figure not shown]
Gilead Sciences, Inc.
[name]
[name]

Study Title:	A Phase 2, Double-Blind, Randomized, Placebo-Controlled Study Evaluating the Efficacy and Safety of Filgotinib in the Treatment of Perianal Fistulizing Crohn's Disease
IND Number:	129646
EudraCT Number:	2016-003153-15
Clinical Trials.gov Identifier:	NCT03077412
Study Centers Planned:	Approximately 60 centers across North America and Europe
Objectives:	
The primary objective of this study is:
 
• To evaluate the efficacy of filgotinib as compared to placebo in establishing combined fistula response at Week 24 
The secondary objectives of this study are:
 
• To evaluate the efficacy of filgotinib as compared to placebo in establishing combined fistula remission at Week 24• To assess the time to clinical fistula response• To assess the time to clinical fistula remission• To evaluate the efficacy of filgotinib as compared to placebo in establishing proctitis remission at Week 24, in subjects that had moderately to severely active proctitis at baseline• To evaluate the safety and tolerability of filgotinib
CC1	 A large block of text has been redacted with a black rectangular box. The word 'CC1' is printed in red above the redacted area.

Study Design:

This is a Phase 2, randomized, double-blind, placebo-controlled study to evaluate the efficacy and safety of filgotinib in treating subjects with perianal fistulizing Crohn's disease (CD). Approximately 75 subjects aged 18 to 75 years with perianal fistulizing CD will be randomized to 1 of 3 treatment groups in a 2:2:1 ratio.

FIL = filgotinib; PBO = placebo; mg = milligram.

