3.3. Study Treatments

Based on protocol eligibility criteria, subjects will be screened for enrollment and randomized into 1 of 3 treatment groups in a blinded fashion in a 2:2:1 ratio as follows:

Treatment group 1 (n = 30): filgotinib 200 mg and PTM filgotinib 100 mg, once daily

Treatment group 2 (n = 30): filgotinib 100 mg and PTM filgotinib 200 mg, once daily

Treatment group 3 (n = 15): PTM filgotinib 200 mg and PTM filgotinib 100 mg, once daily

Note: US males who are not dual refractory will be randomized in a 2:1 ratio to either filgotinib 100 mg or matching placebo. For the purposes of this protocol, US males who have failed at least one prior TNF antagonist AND either previously failed vedolizumab induction therapy or are concomitantly taking vedolizumab at Day 1 and present with actively draining perianal fistulae despite continued vedolizumab therapy will be considered as dual refractory patients. This assessment is based on recently published data from a subgroup analysis of the GEMINI-2 study, showing a beneficial effect of vedolizumab treatment for patients that were randomized with actively draining perianal fistulae at baseline (Feagan 2018).

Treatment assignments will be stratified according to the following factors:

- Anatomy of draining perianal fistulae at screening determined by MRI (simple *versus* complex)
- Receiving vedolizumab therapy concomitantly at Day 1 (Yes or No)
- Presence of moderately to severely active proctitis (Yes or No)

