8.9. Data Monitoring Committee

An external data monitoring committee (DMC) comprised of an independent statistician and two independent gastroenterologists will review the progress of the study and perform interim reviews of safety data and provide recommendation to Gilead whether the nature, frequency, and severity of adverse effects associated with study treatment warrant the early termination of the study in the best interests of the participants, whether the study should continue as planned, or the study should continue with modifications.

The DMC will meet twice to evaluate all available safety data of the study. The initial meeting will occur after approximately 20% of the planned total number of subjects complete their Week 10 visit. Following this, the next meeting will occur after approximately 50% of the subjects reach Week 10. Additionally, the DMC members may request an unscheduled review of the study data based on a concern for subject safety. An ad hoc DMC meeting may be triggered by the following conditions:

- ≥ 2 subjects develop the same (by PT) related, Grade 4, unexpected AE in the infections and infestations SOC
- ≥ 2 subjects develop any related, Grade 4, thromboembolic events that have been positively adjudicated by the adjudication committee (see Section 8.10)
- Any subject develops a Grade 5, related, unexpected AE. The definition of an unexpected AE will be based on the reference safety information that is on file at the time the event occurs

After a minimum of 35 subjects (estimated to be 7 from placebo group and 14 from each filgotinib treatment group based on randomization ratio) are enrolled and complete Week 10 visit or discontinue from the study, an interim futility analysis will be conducted to evaluate efficacy improvement in fistulizing disease. The cumulative safety analysis and summary statistics to evaluate perianal fistula closure of external openings, and CCI [REDACTED]

[REDACTED] improvement will be generated and provided to the DMC. The DMC will make a recommendation to either continue the study without modification or recommend that the study be halted due to lack of efficacy, and will be based on the totality of data available at the time of the interim analysis.

The DMC's specific activities will be defined by a mutually agreed upon charter, which will define the DMC's membership, conduct and meeting schedule.

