#### **2.1.2. Futility Analysis**

After a minimum of 35 subjects (estimated to be 7 from the placebo group and 14 from each filgotinib treatment group based on the randomization ratio) are enrolled and complete the Week 10 visit or discontinue from the study, an interim futility analysis will be conducted to evaluate efficacy improvement in fistulizing disease. The cumulative safety analysis and summary statistics to evaluate perianal fistula closure of external openings, and CCI [REDACTED] will be generated and provided to the DMC. The DMC will make a recommendation to either continue the study without modification or recommend that the study be halted due to lack of efficacy, and will be based on the totality of data available at the time of the interim analysis.

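### The planned arm sizes of 30/30/15, and 14/14/7 at the interim, ignore the US-male 2:1 stream, so the expected 200 mg arm is smaller than stated

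*Protocol*

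**What the plan says.** Two allocation schemes appear in the documents.

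- **Main scheme.** Protocol 3.3 has subjects "randomized into 1 of 3 treatment groups in a blinded fashion in a 2:2:1 ratio" and labels the groups n = 30, 30 and 15. SAP 1.2 repeats this. Protocol 8.8 and SAP 1.3 carry the same sizes: "30 subjects to each of the filgotinib dose groups and 15 subjects to the placebo group".
- **Restricted scheme.** A note directly below the group list in Protocol 3.3, repeated in SAP 1.2, says that "US males who are not dual refractory will be randomized in a 2:1 ratio to either filgotinib 100 mg or matching placebo". The synopsis has a corresponding note. Protocol 1.5 gives the reason, the nonclinical testicular findings, so the restriction is deliberate.

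The interim counts use the main scheme only. Protocol 8.9 has them "estimated to be 7 from placebo group and 14 from each filgotinib treatment group based on randomization ratio", and SAP 2.1.2 says the same: "estimated to be 7 from the placebo group and 14 from each filgotinib treatment group based on the randomization ratio".

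Protocol Table 8-1 (SAP Table 1-1) "provides the exact 90% CI using the binomial distribution for a given combined fistula response rate ranging from 20% to 80" percent. All seven rows are for n = 30, and no arm is named.

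The synopsis plans "Approximately 60 centers across North America and Europe", and SAP 5.1 summarizes US against non-US subjects. Neither document gives the expected number of restricted men, caps that number, or says that enrolment continues until 200 mg reaches 30.

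**The concern.** The planning figures apply one ratio to the whole sample, although the plan itself sends part of the sample through a different ratio that leaves out one arm. The resulting shift has a known direction. Every restricted subject within a fixed total lowers the expected 200 mg arm and raises the other two. That differs from random imbalance around a correct expectation.

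The trial has no formal hypothesis test. Protocol 8.8 justifies the size only as adequate for a descriptive assessment, so the arm sizes and interval widths are the entire justification. If the 200 mg arm is expected to be smaller than 30, the plan shows no interval for the size it should expect there. The interim look, which can lead to a recommendation to halt for lack of efficacy, is likewise described with per-arm counts that the design is not expected to produce.

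**Working it through.** **Inputs.** Total N = 75 (Protocol 8.8) and 35 at the interim (Protocol 8.9). Main ratio 2:2:1 and restricted ratio 2:1 for 100 mg to placebo (Protocol 3.3, SAP 1.2). Exact binomial 90% intervals (Protocol 8.5.1 and 8.8). The number m of restricted US males is not in the documents, so a range is shown.

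**The plan's own figures.** 75 × (2/5, 2/5, 1/5) = 30/30/15, and 35 × (2/5, 2/5, 1/5) = 14/14/7. Clopper-Pearson 90% limits are the 5% quantile of Beta(x, n − x + 1) and the 95% quantile of Beta(x + 1, n − x). At n = 30 they reproduce all seven rows of Table 8-1 to the whole percent; for example, 15/30 gives 33.9–66.1%.

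**Expected sizes under both schemes.**

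- 200 mg: 0.4(N − m)
- 100 mg: 0.4(N − m) + 2m/3
- placebo: 0.2(N − m) + m/3

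Each restricted subject therefore changes the expectations by −0.4 on 200 mg, −0.4 + 0.667 = +0.27 on 100 mg and −0.2 + 0.333 = +0.13 on placebo.

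| N | m | 200 mg | 100 mg | placebo |
|---|---|---|---|---|
| 75 | 0 | 30.0 | 30.0 | 15.0 |
| 75 | 5 | 28.0 | 31.3 | 15.7 |
| 75 | 10 | 26.0 | 32.7 | 16.3 |
| 75 | 15 | 24.0 | 34.0 | 17.0 |
| 35 | 0 | 14.0 | 14.0 | 7.0 |
| 35 | 2 | 13.2 | 14.5 | 7.3 |
| 35 | 5 | 12.0 | 15.3 | 7.7 |
| 35 | 10 | 10.0 | 16.7 | 8.3 |

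To expect 30 on 200 mg, the total T must satisfy 0.4(T − m) = 30, so T = 75 + m.

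**Interval for the 200 mg arm at 50% response.**

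| n | x | exact 90% CI | width (points) |
|---|---|---|---|
| 30 | 15 | 33.9–66.1% | 32.2 |
| 28 | 14 | 33.3–66.7% | 33.4 |
| 26 | 13 | 32.7–67.3% | 34.7 |
| 24 | 12 | 31.9–68.1% | 36.1 |

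**Interval for 200 mg minus placebo**, at assumed rates of 50% and 30%, with the approximate half-width 1.645 × √(0.25/n200 + 0.21/nPBO):

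- m = 0: 1.645 × √(0.25/30 + 0.21/15) = 24.6 points
- m = 15: 1.645 × √(0.25/24 + 0.21/17) = 24.8 points
- m = 22.5 (30% of 75; sizes 21 and 18): 1.645 × √(0.25/21 + 0.21/18) = 25.3 points

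It barely moves because placebo grows as 200 mg shrinks.

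**Chance that 200 mg still reaches 30 or more.** Under simple randomization it is 51% at m = 1, 35% at m = 5 and 19% at m = 10. In a simulation with assumed permuted blocks of 5 and 3 spread over eight strata, it is 52%, 13% and 0.5%. The exact 30/30/15 split occurs in about 9% of those block simulations at m = 1 and 3% at m = 5.

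**The case against.** The strongest defence is that the plan hedges its figures. The total is approximate, 35 is a minimum and the interim counts are estimates. The sponsor may also suspend enrolment at any site or study-wide (Protocol 4.1), so the mix can be managed. This stands in part: such wording covers scatter around an expectation. It does not correct an expectation taken from a ratio that some subjects do not follow.

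Several stronger readings are tempting, and the documents do not support them.

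- *That 30/30/15 cannot occur once one such man is enrolled.* It can, by chance or with a larger total, as the probabilities above show.
- *That Table 8-1 is wrong.* Every row is right for n = 30, and the table names no arm. It would be somewhat optimistic for a smaller 200 mg arm and somewhat conservative for a larger 100 mg arm.
- *That the main dose question suffers most.* The primary objective compares filgotinib with placebo, and Protocol 8.5.1 treats both doses alike.
- *That the monitoring committee would be misled about precision.* It receives summaries of the actual data, the trigger is a total, and no per-arm threshold is stated.

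It is also fair to say that the size of the effect depends on an unknown m. With up to five restricted subjects, the expected loss on 200 mg is at most two.

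**Conclusion.** The point holds as an inconsistency in the planning figures. The sizes 30/30/15 and 14/14/7 are expected only if no restricted US male is enrolled, yet the plan makes specific provision for enrolling them. For any m above zero at a fixed total, the expected 200 mg arm lies below 30, and below 14 at the interim if any of the 35 are restricted. The consequence is modest: over m = 5 to 15, a shortfall of 2 to 6 expected subjects and about 1 to 4 points of added interval width on 200 mg at 50% response. The placebo comparison is almost unchanged, and no power or type I error is affected.

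These sizes rest on a fixed total, an illustrative m, and assumed response rates of 50% for 200 mg and 30% for placebo. The direction of the shift rests on the documents alone.

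**What to change.** In Protocol 8.8 and 8.9 and SAP 1.3 and 2.1.2:

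- State that 2:2:1 applies to subjects outside the US-male 2:1 stream.
- Have the sponsor give its own expected share of restricted subjects. The values of m used here are illustrations and should not be written in as planning figures.
- Restate the expected final and interim arm sizes under both schemes, using the formulas above. Bring the group sizes in Protocol 3.3, the synopsis and SAP 1.2 into line.
- Add rows to Table 8-1 and Table 1-1 for the resulting 200 mg size.

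Rows for the placebo arm and for the difference from placebo would also be useful, because the primary analysis reports that difference. They are optional and do not depend on this defect.

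The cost is text and table edits, with no change to the design or the analysis. The stated size and precision for 200 mg become slightly less favourable.
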